### Rescue medications

If deemed necessary by the treating clinicians, sleep promoting rescue medications may be administered. First choice rescue medication will be melatonin (to be administered no earlier than 3 hours after study drug administration). If this is insufficient, a benzodiazepine may be added for treatment of insomnia (no earlier than 2 hours after melatonin administration). Melatonin and benzodiazepines are drugs of choice for the treatment of insomnia. Haloperidol may be given for agitation, and oxycodone (or dilaudid as second line choice) may be given for pain control as deemed necessary by the primary care team. Dexmedetomidine will not be given to any patient enrolled in the study. Dexmedetomidine will not be used since there is some evidence suggesting that Dexmedetomidine has preventive effects on postoperative delirium [20, 21]. All patients will receive usual supportive care as per the treating physicians and standard practice.

### Questionnaires/Assessments

- Richards-Campbell Sleep Questionnaire (RCSQ): The RCSQ is a validated instrument for assessing sleep and evaluates subjective perceptions of depth of sleep, time to sleep onset, number of awakenings, time spent awake, and overall sleep quality. Each of these five items is assessed using visual analogue scales (each from 0 [worst value] to 100 [best value]). The participant will be asked to use a slider to mark the answer on the scale in the electronic version of the questionnaire or mark an "X" on the paper version.
- Montreal Cognitive Assessment (MoCA): The MoCA Test is a validated tool to quickly assess a patient's cognitive health and detect cognitive impairment. The assessment consists of a one-page test and evaluates several cognitive domains: Short-term memory, visuospatial abilities (clock-drawing), executive functions (trail-marking), attention, language, abstraction, and orientation. The score point values range from 0 [worst] to 30 [best], with 26 and above typically considered "normal" range.
- Confusion Assessment Method (CAM): The CAM is a standardized screening tool used for identification of delirium symptoms. It consist of two parts: Part one screens for overall cognitive impairment, while part two focuses on the 4 features found to have the greatest ability to distinguish delirium from other types of cognitive impairment. Those features of delirium include acute onset and fluctuating course, inattention, disorganized thinking, and altered level of consciousness. The CAM-ICU (a modified version of the CAM for use in ICU patients) includes both brief cognitive testing and the CAM algorithm to screen for delirium.
- Delirium Symptom Interview (DSI): The Delirium Symptom Interview is a standard cognitive assessment assessing areas such as disorientation and perceptual disturbance. The instrument can be administered on a daily basis to track symptoms over time. Each item is scored as present or absent and subscores are created for each assessed area.

**Figure 2.** Illustration of study procedures

## Study endpoints

1. Primary outcome: duration of nighttime wakefulness after persistent sleep onset (WASO) during the first night in the cardiac ICU.
2. Secondary outcome: total sleep time (TST) during the night of the sleep trial in the cardiac ICU.
3. Exploratory outcomes:
  - a) incidence of postoperative in-hospital delirium
  - b) number of delirium free days,
  - c) time to sleep onset (TSO) during the night of the sleep trial,
  - d) effect modification by distinct perioperative factors leading to insomnia in the ICU, such as procedural severity, patients' comorbidities, circadian disruption, and pharmacological treatment with centrally acting drugs.

The following baseline variables will be collected: Clinical and demographic variables will be collected including age, gender, body mass index, type and severity of chronic lung disease, ASA class, history of obstructive sleep apnea, smoking history, hypertension, coronary artery disease, heart failure, cerebrovascular accident or neurologic dysfunction, chronic kidney disease, diabetes mellitus, Charlson comorbidity index and Procedural Severity Score. Additionally, to track other important intraoperative and postoperative factors related to overall patient outcome, we will record administrative, demographic, clinical and billing data including: vital signs, medications administered, length of operation, type of operation, duration of mechanical ventilation, duration of bypass time, total blood loss, blood transfusion, postoperative complications, ICU length of stay prior to drug administration.

We will also record nursing-patient interactions (e.g. intravenous line placement, IV flushing, blood sampling, turning/positioning of patients, wound care, breathing treatments, medication administrations, vital sign checks, neurological checks, point-of-care glucose measurements, and patient-initiated contacts).

## Assessment of study endpoints

### Primary outcome

Sleep and wakefulness will be measured by electroencephalogram (EEG) using a SedLine® Brain Function Monitor during the night of the sleep trial. EEG data will be exported from the SedLine device at the end of the study using an encrypted portable USB storage drive. Data will immediately be transferred to a firewall-protected network drive and deleted from the portable storage. EEG data will be stored on firewall-protected computers as described in detail in section B8. EEG data will be analyzed using dedicated computer software and scored independently by two researchers, blinded to treatment assignment, who will be trained accordingly by a sleep medicine consultant. In case of disagreements between the two researcher's assessments, a sleep medicine consultant will be involved in the scoring. Sleep staging for single channel EEG will then be performed visually with 30 second epoch windows, according to Rechtschaffen & Kales criteria and in accordance with AASM guidelines and differentiated into sleep (REM stage or non-REM stages N1 to N3) and wakefulness (stage 0) [22]. The SedLine Monitor will allow for exclusion of motion-related artifacts by simultaneously capturing EMG signals. A wrist actigraphy will also be used to detect movements during sleep to help trace motion related EEG artifacts more precisely.

Continuous EEG measurements in the ICU may sometimes be prone to artifacts due to electrical interferences arising from devices such as ventilators and infusion pumps, or agitated patients [23]. Therefore, we will also utilize heart rate, respiratory rate and blood pressure reading which are routinely recorded via electronic medical record in the patients enrolled.

Additionally, EEG band power analysis will be performed using fast Fourier transformation (FFT). Briefly, FFT will be performed on all artifact-free EEG epochs visually scored as nonrapid eye movement (NREM) sleep during the entire recording. The average EEG power will be calculated for  $\beta$  (12–30Hz),  $\alpha$  (8–13 Hz),  $\theta$  (4–8

Hz), and  $\delta$  (0.5–4 Hz) frequency bands for each individual patient.

The primary outcome will be Wakefulness After persistent Sleep Onset (WASO). WASO will be defined as the duration of wakefulness after the onset of persistent sleep in the observation period between 10 PM (Lights-Off) to 6 AM (Lights-On) in minutes [24]. Onset of persistent sleep will be defined on the EEG as the first epoch of 10 consecutive minutes of sleep (REM or non-REM Stages 1, 2, 3 or 4) after Lights-Off. Wakefulness will be defined as any epoch of Stage 0.

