#### Exploratory objectives

To determine the effect of postoperative oral suvorexant on postoperative delirium and delirium free days, to evaluate time to sleep onset (TSO) as a measure of sleep onset latency, and to explore patients' comorbidities, treatments, and conditions that may modify the sleep promoting effects of suvorexant in the ICU. We will test the exploratory hypotheses that:

- suvorexant compared with placebo decreases incidence of postoperative in-hospital delirium and increases delirium free days, as measured daily by the Confusion Assessment Method (CAM), CAM-ICU, and the Delirium Symptom Interview until hospital discharge (if CAM screening positive),
- suvorexant compared with placebo decreases TSO during the night of the sleep trial in the cardiac ICU,
- the effect of suvorexant will be modified by distinct perioperative factors leading to insomnia in the ICU, such as procedural severity, circadian disruption, and pharmacological treatment with centrally acting drugs.

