## **B. Statistical Considerations**

### **Sample Size Justification**

We will consider a 30 minute difference in WASO as clinically meaningful, with a standard deviation (SD) of 45 minutes [24]. Accordingly, we expect that a sample size of 50 subjects per group will provide us with >90% power to detect this difference between treatment groups, using a two-sample t-test with 2-sided  $\alpha=0.05$ . As for the exploratory outcome, we may see a difference of 3 delirium-free days (this assumption is based on findings observed with early mobilization by us in a similar cohort [25]) between groups with a SD of 5 days. The given sample size of a total of 100 patients will yield a power of 84.4% to detect a difference in the exploratory

outcome. To account for drop-out, we plan to enroll up to 120 patients to achieve our desired sample size of 100 completed participants.

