### **Data Analysis**

The statistical analyses will be initiated by blinded study team members supervised by a BIDMC statistician. All study personnel will be blinded to the treatment group of the subject, except the investigational pharmacist. For the purpose of the final analysis, unblinding will be performed by the statistician and the research team. The research database will not be unblinded until the medical/scientific review has been completed, protocol violations have been identified (if appropriate), and data collection has been declared as complete.

All analyses will be conducted by research staff supervised by a BIDMC statistician and performed in Stata (StataCorp LP, version 13.0 or higher) and Rstudio (Rstudio.INC, Boston, MA, Version 1.1.4638). All personnel involved in data analyses will be blinded to intervention group assignment. A two-sided P value of <0.05 will be considered statistically significant.

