#### Primary and secondary analyses

The primary and secondary analyses will be by intention-to-treat and will compare WASO and TST between patients receiving suvorexant or placebo. Baseline characteristics of the two groups will be presented descriptively. Normally distributed continuous variables will be expressed as means and standard deviations, non-normally distributed variables as medians and interquartile ranges, and categorical variables as frequencies and percentages. We will calculate the standardized differences of baseline characteristics between the two groups. To determine whether times of WASO and TST differ between treatment groups, we will analyze our data using a Student's t test, or Mann-Whitney-U test, as appropriate.

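### Does the primary analysis break down for a patient who never reaches persistent sleep, and so has no WASO?

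*Combined protocol and SAP*

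**What the plan says.** The section Assessment of study endpoints, Primary outcome, defines the endpoint in two steps. The outcome is wake time after a starting event: "WASO will be defined as the duration of wakefulness after the onset of persistent sleep in the observation period between 10 PM (Lights-Off"; the window closes at 6 AM and the unit is minutes. The starting event is then fixed: "Onset of persistent sleep will be defined on the EEG as the first epoch of 10 consecutive minutes of sleep", counted after Lights-Off, with REM and all non-REM stages accepted as sleep. Nothing is said about a night on which that event does not occur.

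Under Primary and secondary analyses, "The primary and secondary analyses will be by intention-to-treat", comparing WASO and TST by Student's t test or Mann-Whitney U. No rule for missing or undefined values is given. The Sample Size Justification allows for drop-out: "we plan to enroll up to 120 patients to achieve our desired sample size of 100 completed participants".

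Two safeguards are stated. The EEG is "scored independently by two researchers, blinded to treatment assignment", with a sleep medicine consultant brought in when they disagree. In the Data Analysis section, "All personnel involved in data analyses will be blinded to intervention group assignment".

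**The concern.** Both planned tests need one WASO value per patient. A patient with a complete eight-hour recording and no 10-minute run of sleep has not dropped out, yet has no value. Leaving the patient out means selecting on something that happened after randomisation, which sits awkwardly with the intention-to-treat statement. It could also favour one arm if the drug changes who reaches persistent sleep. The Exploratory objectives include the hypothesis that "suvorexant compared with placebo decreases TSO during the night of the sleep trial in the cardiac ICU", which makes an effect on sleep onset a natural worry.

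The setting makes such nights conceivable. The preliminary data under Sleep in the ICU describe short, fragmented sleep after extubation, averaging under 4.5 hours.

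The handling rule could matter. A program that simply counts wake epochs after onset might return 0 for these patients, giving the best possible score to the worst sleepers. At stake would be the size of the primary effect and the power to detect it.

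**Working it through.** **Inputs.** From the Sample Size Justification: difference 30 minutes, SD 45, 50 per arm, two-sided alpha 0.05, up to 120 enrolled. Assumed, because the documents do not give them: the share of patients without persistent sleep (f), the mean WASO (90 vs 60 or 150 vs 120 minutes, placebo vs drug), and how strongly failure to reach persistent sleep goes with severity.

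**Planned power.** Noncentrality = 30 / (45 × √(2/50)) = 30/9 = 3.333, with 98 degrees of freedom and critical value 1.984. Power is 91.0%, which agrees with the plan's claim of more than 90%.

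**How likely is at least one case?** The chance among 100 patients is 1 − (1 − f)^100: 39% at f = 0.5%, 63% at 1%, 87% at 2%, 99% at 5%. So the question could well arise even if such nights are rare.

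**Exclusion, equal share in both arms.** The expected difference stays at 30 minutes if failure is unrelated to severity. Only the sample size falls.

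| f per arm | Analysed per arm | Noncentrality | Power |
|---|---|---|---|
| 0 | 50 | 3.333 | 91.0% |
| 2% | 49 | 3.300 | 90.4% |
| 5% | 48 (47.5 rounded) | 3.266 | 89.8% |
| 10% | 45 | 3.162 | 87.9% |
| 20% | 40 | 2.981 | 83.8% |
| 10% of 60 enrolled | 54 | 3.464 | 93.0% |

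The last row applies if all 120 are enrolled and nobody is lost for any other reason.

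**Exclusion, unequal shares.** These are simulated (8,000 runs, 50 per arm, normal and gamma WASO).

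| f placebo / drug | Correlation of failure with severity | Difference (min) | Power |
|---|---|---|---|
| 10% / 5% | 0 | 30 | 88–89% |
| 10% / 5% | 0.5 to 0.8 | 27–28 | 86–92% |
| 20% / 10% | 0.5 to 0.8 | 24–27 | 79–90% |

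**Scoring 0, which the plan does not propose.** Expected difference = (1 − f_placebo) × mean_placebo − (1 − f_drug) × mean_drug.

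- At 10% vs 5%: 0.90 × 150 − 0.95 × 120 = 135 − 114 = 21 minutes, and 0.90 × 90 − 0.95 × 60 = 81 − 57 = 24 minutes. Simulated power is 45–70%.
- At 1% in both arms: 0.99 × 30 = 29.7 minutes. Power is about 88–90%.

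So at the 1% rate used above to show that the question may arise, even the worst rule costs little.

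**Worst rank, Mann-Whitney, failure unrelated to severity.** Simulated power is roughly 72–85% at 10% in both arms and 88–96% at 10% vs 5%. It keeps every complete recording, but it loses power when the shares are equal and mixes failure to fall asleep into a sleep-maintenance endpoint.

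**The case for a change.** The strongest case for a change is that the gap is certain, the endpoint is primary, and naming a rule would take a sentence or two. Exclusion is not what intention-to-treat normally means. Blinding keeps the choice from being steered by arm, but it does not supply a value. At an assumed 10% vs 5%, the estimated difference is about 21 minutes if these patients are scored 0, 30 if they are excluded and 45 if they are scored 480 (placebo mean 150), so the result is not indifferent to the rule. The source cited for the definition may hold a convention, but it cannot be checked here and, by its title, concerns elderly patients with insomnia rather than ICU patients.

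What stands is that the plan is silent, and that exclusion would make the comparison in minutes conditional on reaching persistent sleep. The rest is weaker.

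- The spread from 21 to 45 minutes comes from two scores that the plan does not suggest. A WASO of 0 for someone who hardly slept should be evident to two scorers who stage every epoch.
- The hypothesis on time to sleep onset is exploratory and concerns latency. Falling asleep sooner does not imply that a different share of patients goes eight hours without a 10-minute run of sleep. A difference between arms is possible but is not something the plan predicts.
- The preliminary data cut both ways. Sleep was fragmented, but patients averaged hours of it, mostly in stages 1 and 2, which the definition counts as sleep.
- Writing down exclusion would state what the definition already implies. Making worst rank primary would exchange one weakness for another.

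A related point is recordings spoiled by interference: "Continuous EEG measurements in the ICU may sometimes be prone to artifacts due to electrical interferences". Those are ordinary missing data. They are a different matter from a clean recording without persistent sleep, and analysts can be expected to keep the two apart.

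**Conclusion.** No change to the plan is needed. The documents leave a detail unstated, and competent analysts would fill it sensibly: a patient without persistent sleep has no WASO in minutes, is not given 0, and is counted and reported by arm. A supportive ranking of all complete recordings would be reasonable, as would a look at TST, which in its usual sense (all sleep in the window) exists for such a patient too. These are choices for a blinded data review, and adding them to the text would correct no wrong result.

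On the natural reading the size is small. Exclusion costs about 3 percentage points of power at 10% in both arms (91.0% to 87.9%), and the enrolment margin could cover that. The difference shrinks by 2 to 3 minutes at 10% vs 5% if failure goes with severity, and by 3 to 6 minutes at 20% vs 10%.

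This rests on assumed rates, WASO means and distribution shapes, since the documents give none. The conclusion would weaken only if such nights proved common and clearly unequal between the arms, which the reported counts would show.

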#### Secondary outcome

Secondary outcomes will include total sleep time (TST) measured during the night of the sleep trial by using electroencephalography (EEG), in analogy to the primary outcome.

#### Exploratory outcomes

*Time to sleep onset (TSO)* during the night of the sleep trial will be assessed using electroencephalography.

*Subjective sleep quality* will be assessed by applying the Richards-Campbell Sleep Questionnaire (RCSQ). The RCSQ is a validated survey instrument for assessing sleep quality in critically ill patients based on a five-item, visual analogue scale (each from 0 [worst value] to 100 [best value]) [8]. The scale evaluates perceptions of depth of sleep, sleep onset latency, number of awakenings, time spent awake, and overall sleep quality.

#### *Delirium*

Incidence of postoperative delirium and delirium-free days during the hospitalization (capturing days in the ICU and on the hospital ward) will be assessed. Delirium assessments will be performed daily until hospital discharge using the Confusion Assessment Method (CAM) or CAM-ICU [19]. Assessments will be performed by nursing staff as part of routine clinical care, or a research team member trained in the survey administration methodology and blinded to treatment assignment. The CAM is a standardized screening tool used for identification of delirium symptoms through a diagnostic algorithm based on 4 cardinal features of delirium, namely acute onset and fluctuating course, inattention, disorganized thinking, and altered level of consciousness. The CAM-ICU, which is routinely performed in the ICU, includes both brief cognitive testing and the CAM algorithm to screen for delirium. For CAM-positive patients, the Delirium Symptom Interview, a standard cognitive assessment consisting of tests of attention, orientation, and memory will be performed by a research team members trained in the survey administration methodology and blinded to treatment assignment to verify the CAM screening results.

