### **Delirium in the ICU**

Delirium is a syndrome of acute organ dysfunction occurring in up to 50% of ICU patients [15], which carries financial and societal burdens due to its association with increased morbidity, mortality, and prolonged hospital stays. The occurrence of ICU delirium predicts a 3 to 13-fold rise in the likelihood of death within one year after adjusting for severity of illness, coma, sedatives, and other relevant covariates [16]. Delirium is usually multifactorial, and sleep deprivation is a contributing mechanism.

It has been reported that suvorexant may have preventive effects on postoperative delirium [17]. However, the published evidence is poor, since sleep in those studies was not formally assessed using objective methods and subjective assessments failed to identify an effect of suvorexant on sleep onset or maintenance. Also, the incidence of delirium was surprisingly low in this study (< 10 percent), and no patient in the intervention group developed delirium [17]. These are surprising findings which are at odds with the sound biological concepts and results of published, carefully conducted studies. It is frankly hard to believe that suvorexant given at a dose that does not improve sleep quality eliminates delirium in the ICU. The effect of suvorexant on postoperative delirium in the intensive care unit in patients after cardiac surgery were analyzed and recently published [18]. The authors reported that following routine use of suvorexant 20 mg, only one patient out of 36 presented with postoperative delirium, as compared to 11 of 52 patients prior to the introduction of suvorexant. The small

sample size and insufficient confounder control limit the value of this study. In addition, sleep was not quantified - so as of today, it is unclear as to whether the observed, numerical reduction in postoperative delirium rate by suvorexant is the consequence of improved sleep quality.

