### Assessment of delirium

In this study, delirium will be assessed daily using the Confusion Assessment Method (CAM) or CAM-ICU for reintubated patients [19]. The CAM is a standardized tool for screening purposes based on the four core features of delirium: acute onset and fluctuating course, inattention, disorganized thinking, and altered level of consciousness. The CAM is implemented into routine clinical practice at our institution. In addition, to verify the CAM screening results in CAM-positive patients we will perform the Delirium Symptom Interview, a diagnostic set of tests evaluating attention, orientation, and memory [19]. We have recently conducted and published a randomized clinical trial investigating effects of intravenous acetaminophen on postoperative delirium at our institution, which successfully utilized the same methods of outcome assessment [19]. Given the importance of insomnia and delirium in the ICU, there is a need for a well-designed study that examines the effects of suvorexant on sleep and delirium in critically ill patients. Our study will inform the effect size calculation for those future trials.

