#### Delirium in the ICU

Based on our study conducted in a similar cohort [19], we expect an incidence of delirium of 28.3% with an average of 20-25 delirium free days during the hospital stay. We further examined our data obtained in the cardiovascular ICU and found that the incidence of delirium was similar for patients undergoing isolated coronary artery bypass graft (44/179, 24.6%) and coronary artery bypass with aortic (8/32, 25.0%) or other (2/9, 22.2%) cardiac valve replacement surgery.

**Figure 1.** Administration of sedatives and opioids during nighttime (6 PM - 6 AM) in ICU patients admitted to Beth Israel Deaconess Medical Center (BIDMC) ICU for more than 48h in 2017.

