## B3. DESCRIPTION OF RESEARCH PROTOCOL

### A. Study Design – Overview, Methods, Procedures

#### Study design & overview

- This is a single-center, randomized, double-blind, placebo-controlled trial expected to enroll 120 subjects. Participants will be enrolled preoperatively and randomized in a 1:1 ratio to receive suvorexant or placebo. Prior to randomization, informed consent will be obtained from all participants. The patient is first asked to report information about their sleep using the Richards-Campbell Sleep Questionnaire (RCSQ). Patients will be asked to complete a sleep questionnaire for at least one night before surgery or, if possible, daily, starting 3 days before surgery. The questionnaire will be performed online in RedCap; patients will be emailed a link to the survey. If patients do not have access to an internet-enabled device, they will be handed the RCSQ on paper and asked to complete it before surgery. The intervention (study drug) will be applied for 7 nights starting the night after postoperative extubation in the ICU. Primary and secondary outcomes will be assessed once during the night of the sleep trial in the ICU. The sleep trial will take place during the first night after extubation if the patient has been extubated before 7pm. If patient is extubated after 7:00 pm study medication will be administered the night after extubation only if still in ICU.

Exploratory outcomes will be assessed from day of extubation until hospital discharge. An outline of the study procedures is provided in **Figure 2**.

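### Delirium-free days are counted only until discharge, with no common window and no rule for discharge or death, so the exploratory score mixes delirium with length of stay

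*Combined protocol and SAP*

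**What the plan says.** The Study endpoints list (B3.A) names the "number of delirium free days" as an exploratory outcome, without a window. The Delirium paragraph under Assessment of study endpoints describes it as "delirium-free days during the hospitalization (capturing days in the ICU and on the hospital ward" and adds: "Delirium assessments will be performed daily until hospital discharge". The start point comes from Study design & overview: "Exploratory outcomes will be assessed from day of extubation until hospital discharge".

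The Exploratory objectives (B1) attach a directional hypothesis: "suvorexant compared with placebo decreases incidence of postoperative in-hospital delirium and increases delirium free days". The Delirium paragraph of the exploratory analyses (B3.B) refers to the methods of the primary and secondary analyses, which are a Student's t or Mann-Whitney test. No section fixes a number of days, scores days after discharge, scores in-hospital death or adjusts for length of stay.

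Three planning figures bear on the outcome. The preliminary data (B2) state: "we expect an incidence of delirium of 28.3% with an average of 20-25 delirium free days during the hospital stay". The Sample Size Justification assumes a 3-day difference with an SD of 5 days and gives 84.4% power for 100 patients. The Study interventions section foresees that some patients leave hospital fewer than 7 days after extubation.

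**The concern.** When counting stops at discharge, each patient has a different maximum score. A patient without delirium who goes home on day 5 scores 5. A patient with 3 delirious days who goes home on day 10 scores 7. The worse course gets the better score.

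This can do harm in two ways. First, ordinary variation in stay enters the score as noise. Second, the background section (B2, Delirium in the ICU) notes delirium's "association with increased morbidity, mortality, and prolonged hospital stays". If part of that association is causal, preventing delirium would remove hospital days as well as delirious days, and the two changes move the score in opposite directions.

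The outcome is exploratory, but it carries a hypothesis and a power statement, and the Assessment of delirium section says: "Our study will inform the effect size calculation for those future trials". An effect size that partly measures length of stay is a poor basis for planning another trial.

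**Working it through.** **1. The plan's own power.** Difference 3, SD 5, 50 per arm, two-sided 0.05: standardised effect 3/5 = 0.6, 98 degrees of freedom, noncentral t. Power is 84.39%, so the stated 84.4% reproduces. The arithmetic is sound; the scale of its inputs is what is undefined.

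**2. Inputs for the illustration.** From the documents: incidence 28.3%, 50 per arm, two-sided 0.05. Assumed, because the documents give no figure: suvorexant halves incidence (a drop of 0.283 × 0.5 = 0.1415), D delirium days per case, L extra hospital days per case, the SD of stay, and no deaths.

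**3. Mean difference as written.** Score = stay − delirium days, so the arm difference is 0.1415 × (D − L) days:

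| D | L = 0 | L = 2 | L = 3 | L = 5 |
|---|---|---|---|---|
| 2 | +0.28 | 0.00 | −0.14 | −0.42 |
| 3 | +0.42 | +0.14 | 0.00 | −0.28 |
| 5 | +0.71 | +0.42 | +0.28 | 0.00 |

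At L = 0 the full difference is kept. It shrinks for 0 < L < D, vanishes at L = D and changes sign for L > D.

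**4. Precision when stay is unaffected (L = 0, mean D = 3).** The difference is 0.1415 × 3 = 0.4245 day.

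- Every case lasts exactly 3 days: the variance of delirium days is 9 × 0.283 × 0.717 = 1.826 on placebo and 9 × 0.1415 × 0.8585 = 1.093 on suvorexant. The average is 1.460, so SD 1.21.
- Duration varies as 1 + Poisson(2): the mean is 3 and the mean square is 2 + 9 = 11. The variances are 11 × 0.283 − 0.849² = 2.392 and 11 × 0.1415 − 0.4245² = 1.376. The average is 1.884, so SD 1.37.

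Adding an independent variance of stay gives this t-test power:

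| SD of stay in the score | Fixed duration: total SD, power | Varying duration: total SD, power |
|---|---|---|
| none | 1.21, 41% | 1.37, 33% |
| 2 days | 2.34, 15% | 2.43, 14% |
| 4 days | 4.18, 8% | 4.23, 8% |

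A separate simulation (5,000 trials, assumed stay of mean 7 and SD 3 days, varying duration) agrees: power was about 34% over a fixed 28-day window and about 9% for the in-hospital count.

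**5. Do the planning figures fit an in-hospital count?** A score that cannot exceed the stay and averages 20-25 requires a mean stay of at least 20-25 days, yet the plan also provides for discharge within a week of extubation. With no effect on stay, a 3-day mean difference needs 3/0.283 = 10.6 delirium days per case even if every case is prevented, or 3/0.1415 = 21.2 if incidence is halved. The fit is poor, and the documents do not state the window for these figures.

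**6. Length of a fixed window.** With a window of W days and onset on day o of it, the difference is 0.1415 × min(D, W − o + 1), not below 0. For D = 3, the full +0.42 needs onset by day 5 of a 7-day window or day 12 of a 14-day window. For D = 5, the full +0.71 needs onset by day 3 or day 10. Too short a window also dilutes the effect.

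**The case against.** A reader might infer that the count necessarily hides a benefit or is biased against suvorexant. The documents do not support that. With equal stay in the two arms the mean difference is intact and only precision suffers. Bias needs a causal effect of delirium on stay; the background section reports an association only, and no document figure shows that L exceeds D.

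The scoring formula is also inferred. The plan says when delirium is assessed and that in-hospital days are counted, but writes out no formula, and the 20-25 days may come from a differently defined count in the earlier study. That leaves the formula as the natural reading rather than a stated equation. It does not remove the need for a definition.

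Nor may one conclude that the 84.4% ignores variation in stay. An SD of 5 may already contain it: adding a stay SD of 5 to the fixed-duration case gives a total of 5.14.

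Finally, the consequence is limited. The outcome is exploratory, delirium incidence is listed separately, and the daily assessments would allow a different count later. All of this stands. It lowers the priority, although a window chosen after the data are seen is worth less than one chosen beforehand.

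**Conclusion.** The point holds as an optional but worthwhile improvement. Followed as written, the plan gives an exploratory score that depends on length of stay, with no common window and no rule for discharge or death. If stay is unaffected, the cost is precision: power of about 33-41% falls to about 14-15% or 8% for a stay SD of 2 or 4 days. If preventing delirium also shortens stay, the cost is dilution, and reversal once L exceeds D. Apart from the 28.3% incidence, the sample size and the significance level, the inputs are assumptions, so these sizes are illustrations and not forecasts. The primary and secondary sleep analyses, and the sample size set for WASO, are unaffected.

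**What to change.** In Study endpoints and in the Delirium paragraph of Assessment of study endpoints, define the outcome as days alive and free of delirium over one fixed window, the same for every patient.

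- **Start:** randomization or the first scheduled study-drug night. The day of extubation is unsuitable, because randomization and the evening dose come after extubation and patients who are CAM-ICU positive at drug initiation are excluded.
- **Length:** for example 14 days, chosen from the investigators' own data on delirium onset and duration.
- **Live discharge:** state the rule, for example later days count as delirium-free, with a sensitivity analysis for patients who are CAM-positive at their last assessment.
- **In-hospital death within the window:** state the rule, for example a score of 0.
- **Alongside:** report in-hospital delirium days and length of stay by arm.

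In the preliminary data and the Sample Size Justification, state the window to which 20-25 days, 3 days and SD 5 refer. Re-derive the 84.4% for the chosen window or delete it.

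The cost is a few sentences; the daily delirium data are already collected. There are two downsides. Patients discharged before the window closes are assumed alive and delirium-free, because the plan describes no delirium follow-up after discharge. Power also stays modest, about 33-41% by t-test under the assumptions shown.
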